1.3.2 Safety Endpoints

- The incidence, severity, and relationship to the investigational device of all reported adverse events
- 118 (serious and non-serious including DKA and severe hypoglycemia) from day of insertion through day
- of device removal for each wear period.

1.3.3 Key Secondary Endpoint

- Proportion (%) of SteadiSet infusion sets withdrawn from use at any time following insertion prior to 7
- days (168 hours) as evidenced by one or more of the following device failure modes. NOTE: infusion set
- removals prior to 168 hours due to miscalculation of date and/or time, along with other removals that
- cannot be ascribed to the investigational device performance, are excluded from this proportion
- 125 calculation.

126 1. Infusion set failure as defined in the Primary Endpoint (including any such removals occurring during the first 8 hours following set insertion) 127 2. Evidence of infusion set site infection defined as requiring treatment or at the investigator's 128 iudgment 129 3. Cannula dislodgement from subcutaneous (SC) space (with or without liquid leakage at the 130 cannula insertion site) 131 132 a. Leakage at the cannula insertion site may or may not be deemed by the investigator to constitute infusion set failure following consultation with the study subject 133 b. Accidental removal events (e.g., tubing caught on doorknob) are excluded from this 134 proportion calculation 135 136 4. Occurrence of a non-resolvable pump occlusion alarm 5. Other device malfunction (e.g., inability to pierce skin, bending, or other malformation that might 137 impact insulin infusion, securement failure) 138 6. Presence of pain of sufficient severity to prompt early removal of infusion set 139 7. Any other event that can be ascribed to the investigational device performance that results in 140 failure of insulin delivery 141 1.3.4 Other Secondary Endpoints 142 1. Standard glucose control metrics obtained from CGM, including hyper- and hypoglycemic 143 episodes, time in range, mean 24-hour glucose, and other measures 144 2. Total daily insulin dose, basal dose, bolus dose, and bolus basal ratio, overall, and by day of 145 infusion set wear 146 147 3. Subject tolerability levels for the infusion set insertion as assessed by a pain scale of 0 to 100 with zero being no pain and 100 being significant pain 148 4. Hyperglycemia trends in days 1-3 versus after day 3 149 5. Infusion set performance (including set failures as defined above and also glucose metrics, 150 insulin doses, pump occlusion alarms and hyperglycemia trends) in subjects who use low doses 151 (e.g., <25 units/day) of insulin and in subjects who experience frequent stops and start of pump 152 use 153 1.3.5 Exploratory Endpoint 154 1. HbA1c change from baseline to the end of study participation. 155 1.4 Subject Hyperglycemia Management and Infusion Set Removal 156 Guidelines 157 1. If, in the absence of illness or other physiological stress, blood glucose is ≥250 mg/dL and 158 ketones are >1.0 mmol/L, then infusion set failure is established.* 159 o Ketones are to be measured any time the blood glucose value is ≥250 mg/dL 160 If ketones are elevated the subject should test ketones hourly until ketones fall below 161 0.6 mmol/L. 162

204

205

JAEB CENTER FOR HEALTH RESEARCH

163 164 165	snack or m	M glucose value is \geq 250 mg/dL for 60 minutes or longer, 3 hours or more following a neal event AND ketones measure \leq 1.0 mmol/L then attempts to correct the emia are to occur as follows:
166	0	Confirm the blood glucose value is ≥250 mg/dL with a fingerstick BG value.
167 168	0	If this fingerstick BG value is <250 mg/dL the subject will be instructed to continue to follow CGM readings.
169 170		firmatory fingerstick BG value is ≥250 mg/dL then an initial manual correction bolus red by the pump is to be given using the fingerstick BG value.
171 172 173 174 175 176	hourly initial second (The n	nutes from the initial correction bolus (not the time of an auto bolus) will start the testing schedule for fingerstick BGs and ketones. If the repeat ketone level after the correction bolus is ≤1.0 mmol/L, and the glucose has not fallen by 50 mg/dL then a discorrection bolus should be administered using the same procedures described above. In an all correction bolus dose given from the Bolus Calculator the subject administers whe into consideration the estimated residual Insulin on Board)
177 178 179 180	0	If a repeat fingerstick BG value shows failure to respond to the second correction bolus within an additional hour with a fall of 50 mg/dL from the fingerstick BG prior to initial correction bolus and there has been no intervening snack or meal event , then the infusion set failure is established.*
181 182 183 184	0	If the fingerstick BG has responded to the second correction bolus with a fall of at least 50 mg/dL from the fingerstick BG prior to the initial correction bolous AND the fingerstick BG is still ≥250 mg/dL then fingerstick BGs and ketone levels should be rechecked hourly until the fingerstick BG level falls below 250 mg/dL.
185 186 187	0	If fingerstick BG does not fall below 250 mg/dL within six (6) hours from initial hyperglycemic event (i.e., 9 hours after a meal event) infusion set failure is established*.
188 189	0	If the ketone level measures >1.0 mmol/L at any of these hourly rechecks, then the infusion set is deemed to have failed.*
190 191 192	contact the	eve scenarios occur prior to 174 hours of infusion set wear, the subject is required to study site to confirm set failure prior to removing the infusion set and provide n to the study site regarding circumstances around the event.
193 194 195 196	happens, t	rsonnel are not available the subject should remove and replace the infusion set. If this ne subject will need to contact the study site at their earliest convenience to provide the onnel with detailed information regarding the events surrounding the infusion set
197 198 199	procedure	study site personnel have been contacted (either during the infusion set change or afterwards), they will conduct a structured interview and document the relevant n in the eCRF.
200 201		functioning satisfactorily after 174 hours, then subject may take up to 18 additional e set. In no case should the set be worn beyond 192 hours of use.
202		1.5 Potential Risks and Benefits of the Investigational Device System
203	Risks and benefits	are detailed below. Loss of confidentiality is a potential risk; however, data are

handled securely to minimize this risk. Hypoglycemia and hyperglycemia are always a risk in subjects

with type 1 diabetes and insulin treatment, and subjects will be monitored for this.

206 207 208 209	The SteadiSet device has been analyzed for possible hazards using the methods in ISO 14971:2012 Medical Devices, Application of Risk Management to Medical Devices. Capillary Biomedical Inc. considers SteadiSet to be adequately safe to justify its use in clinical trials based on the benefits compared to overall risk.
210	1.5.1 Known Potential Risks
211	1.5.1.1 Risk of Hypoglycemia
212 213 214 215 216 217	As with any person having type 1 diabetes and using insulin, there is always a risk of hypoglycemia. The frequency of hypoglycemia should be no more than it would be as part of daily living. Symptoms of hypoglycemia can include sweating, jitteriness, and not feeling well. Severe hypoglycemia is possible with loss of consciousness or seizures. Recurrent hypoglycemia may reduce hypoglycemia awareness. A CGM functioning poorly and significantly over-reading glucose values could lead to inappropriate insulin delivery.
218	1.5.1.2 Risk of Hyperglycemia
219 220 221	Hyperglycemia and ketonemia could occur if insulin delivery is attenuated or suspended for an extended period or if the pump or infusion set is not working properly. A poorly functioning CGM significantly under-reading blood glucose values could lead to inappropriate suspension of insulin delivery.
222	1.5.1.3 Insulin Infusion Risks
223 224	The study infusion set is inserted under the skin. Infection can occur very infrequently, but, if an infection was to occur, oral and/or topical antibiotics can be used to treat the infection.
225 226	Examples of possible infusion site reactions include: localized pain, bleeding, bruising, induration, infection, itching/pruritus, purulence, reddening (erythema), swelling, and other non-specified irritation.
227 228 229 230 231 232	Infusion set failure may occur, leading to hyperglycemia or ketosis. The risk for infusion set failure may be increased in this study because sets are worn for an extended period. Examples of insulin infusion failure modes include: clogs, accidental removal, insulin leak from site, insulin leak from set or tubing, adhesive failure, cannula insertion failure (not all holes below epidermis), incomplete tubing prime, incomplete cannula prime, air bubbles in tubing, inadequate insulin pump/cartridge/infusion set connection, and cannula inserted too deep.
233	1.5.1.4 Risks of Use of Insulin Pump with Automated Insulin Delivery
234 235	CGM sensor readings higher or lower than the actual blood glucose level increases the risk for hypoglycemia and hyperglycemia with use of automated insulin delivery systems.
236 237	Algorithm or other device malfunctions could produce a suspension of insulin delivery or over-delivery or insulin which increases risk for hyperglycemia and hypoglycemia.
238	1.5.1.5 Fingerstick Risks
239 240 241 242 243	About 1 drop of blood will be removed by fingerstick for measuring HbA1c or doing other tests. Pain is common at the time of lancing. In about 1 in 10 cases, a small amount of bleeding under the skin will produce a bruise; a small scar may persist for several weeks. The risk of local infection is less than 1 in 1000. This should not be a significant contributor to risks in this study as finger sticks are part of the usua care for people with diabetes.

244	1.5.1.6 CGM Subcutaneous Catheter Risks
245 246 247	Use of CGM has a low risk for developing a local skin infection at the site of the sensor needle placement. There may be bleeding where the catheter is put in and bleeding under the skin causes a bruise (1 in 10 risk).
248 249	On rare occasions, the sensor may break and leave a small portion of the sensor under the skin that may cause redness, swelling or pain at the insertion site.
250	1.5.1.7 Risks Associated with Device Reuse
251 252	In this study, device components (CGM, BG meter, or ketone meter) will not be reused between different subjects.
253	1.5.1.8 Rapid-Acting Insulin Analog Adverse Reactions
254 255 256 257 258	Study subjects must be current users of rapid-acting insulin analogs at the time of enrollment (i.e., completion of consent documentation). Therefore, the risk of adverse reactions to commercially available rapid-acting insulin used during the study should be very low, but development of the following conditions is possible: anaphylaxis, antibody production, hypokalemia, lipodystrophy, peripheral edema, renal or hepatic impairment, and weight gain.
259	1.5.1.9 Questionnaire-Associated Risks
260 261 262 263	As part of the study, subjects will complete questionnaires which include questions about their private attitudes, feelings and behavior related to the investigational equipment as well as managing diabetes. It is possible that some people may find these questionnaires to be mildly upsetting. Similar questionnaires have been used in previous research and these types of reactions have been uncommon.
264	1.5.1.10 Other Risks
265 266	Some subjects may develop skin irritation or allergic reactions to the adhesives used to secure the CGM, or to secure the insulin infusion sets for the continuous subcutaneous insulin infusion.
267 268 269	Data uploaded from the subject's pump, CGM and study blood glucose and ketone meter will be collected for the study as measures of diabetes self-management behaviors. Some people may be uncomfortable with the researchers' having such detailed information about their daily diabetes habits.
270 271	There may be other risks that are unknown at this time and new risks that may be identified during the study.
272 273	The infusion set has not been tested with radiation therapy or an MRI procedure. The infusion set should be removed before radiation therapy or an MRI procedure.
274	1.5.2 Known Potential Benefits
275 276 277	Study participation may not provide any immediate benefit to study subjects. However, results of this research may result in the following potential benefits to the study subjects or to future patients with diabetes:
278	 Development of an extended wear insulin infusion set
279	 Reduction in the number of required infusion set insertions and number of infusion sites
280	 Reduction in infusion site (skin/tissue) reactions
281	 Improved glucose control (e.g., more stable insulin kinetics)

282	 Improved Continuous Subcutaneous Insulin Infusion (CSII) and insulin pump therapy options
283	 Reduced environmental waste
284	1.5.3 Risk Assessment
285 286 287	It is the assessment of the investigators that this protocol falls under DHHS 45 CFR 46.406 and 21 CFR 50.53 as a clinical investigation involving greater than minimal risk and no prospect of direct benefit to individual subjects, but likely to yield generalizable knowledge about the subjects' disorder or condition.
288	1.6 General Considerations
289 290 291	The study is being conducted in compliance with the policies described in the study policies document, with the ethical principles that have their origin in the Declaration of Helsinki, with the protocol described herein, and with the standards of Good Clinical Practice (GCP).
292 293 294	The protocol is considered a significant risk device study since the study infusion set is experimental. Therefore, an investigational device exemption (IDE) from the U.S. Food and Drug Administration (FDA) is required to conduct the study.

295	Chapter 2: Study Enrollment and Screening
296	2.1 Subject Recruitment and Enrollment
297 298 299 300 301	Enrollment will proceed with the goal of 240 subjects (120 each on insulins lispro and aspart) completing the main study phase involving use of the study infusion set. A maximum of 300 individuals may be consented for screening to achieve this goal. Subjects who complete at least six wear periods will be considered as completers. Subjects who have signed consent and started the screening process may be permitted to continue into the trial, if eligible, even if the goal of 240 completers has been reached.
302 303 304 305 306	Study subjects will be recruited from up to 20 clinical centers in the United States. All eligible subjects will be included without regard to gender, race, or ethnicity. Each site may contribute a maximum of 25 subjects toward the target of 240 who complete the main study phase. If the enrollment of one insulin type reaches its enrollment goal, that insulin cohort may be closed and only subjects using the insulin in the other insulin cohort would then be eligible for study enrollment.
307	2.1.1 Informed Consent and Authorization Procedures
308 309 310 311	Potential eligibility may be assessed as part of a routine-care examination or via interaction with the potential subject following a direct inquiry (e.g., resulting from IRB-approved recruiting materials) or a referral from another source. Before completing any procedures or collecting any data that are not part of usual care, electronic informed consent will be obtained.
312 313 314 315 316 317 318	The potential study subject will be provided with the Informed Consent Form to read and will be given the opportunity to ask questions either in-person, via phone/videoconference, or by mail or email. If the potential subject is interested in the study, the investigator will schedule a virtual or in-person visit to discuss the study, and if the potential subject agrees to participate, that individual will electronically sign the Informed Consent Form through the JCHR study website, and the enrolling investigator will also electronically sign the document. A copy of the electronically signed consent form can be printed by the subject and another copy will be printed by the site to add to the subject's study record.
319 320 321 322 323	As part of the informed consent process, the subject will be asked to sign an authorization for release of personal information. This may be done electronically with the consent, or on paper if the site requires their own process. The investigator, or his or her designee, will review the study-specific information that will be collected and to whom that information will be disclosed. After speaking with the subject, questions will be answered about the details regarding authorization.
324 325 326	A subject is considered enrolled when the informed consent form has been electronically signed by all parties and HIPAA authorization has been provided. No study procedures may be performed before the completion of the informed consent documentation.
327	2.2 Subject Inclusion Criteria
328	Individuals must meet the following inclusion criteria to be eligible to participate in the study.
329	1. Age 18 to 80 years old inclusive
330	2. Generally, in good health, as determined by the investigator
331	3. Living in the United States with no plans to move outside the United States during the study
332	4. Diagnosis of T1D for at least 12 months
333 334	5. Minimum of 6 months of insulin pump experience and at least 3 months of current experience with a Tandem pump

- 6. Using Tandem t:slim X2 insulin pump with Control-IQ technology for a minimum of 1 month at the time of enrollment
- 7. Minimum of 14 days of Control-IQ data immediately preceding screening that demonstrate pump use compliance, including at least 85% of time with Control-IQ technology active
- 8. HbA1c < 9.0% in the last 6 months
- 9. Willing to implement and adhere to pump alert/alarm settings on a study-provided pump as instructed during the study
- 342 10. Willing to wear each investigational infusion set for up to 7 days during each of the 12 consecutive wear periods in the study
- 11. Willing to perform blood ketone and blood glucose (fingerstick) measurements as directed using provided ketone and blood glucose meters and strips
- 12. Access to internet for required periodic uploads of study device data
- 13. BMI in the range 18–35 kg/m2, both inclusive
- 14. Currently using one of the following insulins with no expectation of a need to change insulin type during the study:
- a. HumalogTM (insulin lispro)
- b. NovoLogTM (insulin aspart)
- 15. Using HumalogTM insulin lispro or NovoLogTM insulin aspart for a minimum of 1 month at the time of enrollment
- 16. Willing to change insulin cartridge every 48-72 hours, as recommended by patient's healthcare provider during the study
 - 17. Has routine access to a smart phone e.g., ability to receive text messages
- 18. Has the ability to understand and comply with protocol procedures and to provide informed consent (i.e., English proficient in both verbal and written communication)

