Objectives	Primary Objective: ◆ The evaluation of SteadiSet device function as evidenced by the absence of device failure due to uncontrolled hyperglycemia with or without ketosis Secondary Objectives: ◆ Characterization of safety endpoints, glycemic control and insulin dosing while using the SteadiSet device
Study Design	Prospective, Multi Center, Single Arm study
Number of Sites	Up to 20 sites in the United States
Endpoint	Primary Efficacy Endpoint: Percentage of successfully inserted SteadiSet infusion sets (i.e., not removed within 8 hours of insertion) that are not withdrawn from use prior to 7 days (168 hours) due to either (1), (2), or (3): 1. Blood Glucose value ≥250 mg/dL with ketones >1.0 mmol/L, in the absence of
	 illness or other physiological stress. 2. Blood Glucose value ≥250 mg/dL for at least 60 minutes duration, 3 hours or more following a snack or meal event AND failure to respond to up to 2 adequate corrective boluses delivered by the pump with a fall of at least 50 mg/dL.
	3. Investigator advises the infusion set should be replaced to assure subject's safety
	See Section 1.4 Subject Hyperglycemia Management and Infusion Set Removal Guidelines for additional details.
	A Clinical Events Committee (CEC) will adjudicate primary and secondary clinical endpoint events based on review of all available information that is relevant to determine whether protocol-defined endpoint events have occurred during the study. See Section 8.4.1 Clinical Events Committee for additional details.
	Safety Endpoints:
	The incidence, severity, and relationship to the investigational device of all reported adverse events (serious and non-serious including diabetic ketoacidosis (DKA) and severe hypoglycemia) from day of insertion through day of device removal for each wear period.
	Key Secondary Endpoint:
	Proportion (%) of SteadiSet infusion sets withdrawn from use at any time following insertion prior to 7 days (168 hours) as evidenced by one or more of the following device failure modes. NOTE: infusion set removals prior to 168 hours due to miscalculation of date and/or time, along with other removals that cannot be ascribed to the investigational device performance, are excluded from this proportion calculation.
	Infusion set failure as defined in the Primary Endpoint (including any such removals occurring during the first 8 hours following set insertion)

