1.3 Endpoints

1.3.1 Primary Efficacy Endpoint

- Percentage of successfully inserted SteadiSet infusion sets (i.e., not removed within 8 hours of insertion) that are not withdrawn from use prior to 7 days (168 hours) due to either (1), (2), or (3):
 - 1. Blood Glucose value ≥250 mg/dL with ketones >1.0 mmol/L, in the absence of illness or other physiological stress.
 - 2. Blood Glucose value ≥250 mg/dL for at least 60 minutes duration, 3 hours or more following a snack or meal event AND failure to respond to up to 2 adequate corrective boluses delivered by the pump with a fall of at least 50 mg/dL.
 - 3. Investigator advises the infusion set should be replaced to assure subject's safety

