458 459 460 461	A capillary blood sample will be obtained for baseline HbA1c determination. For remote subject's capillary collection, supplies will be provided to the subject within 3 days of the Study Infusion Set Initiation Visit. Collection of HbA1c may occur either in-person at the clinic, or via delivery by other means (personal delivery, overnight shipment, etc.).
462	3.1.2 Study Infusion Set Training and Initiation
463 464	Subjects will be trained (in-person or via videoconference) on how to insert the SteadiSet infusion set. The initial insertion will be observed either in person or on video during a virtual visit.
465 466	Subjects who are unable to insert the SteadiSet within 3 attempts will be dropped from study participation.
467	Points of training will include the following:
468 469	 Subjects will be advised to avoid inserting the SteadiSet device in places that may cause pressure—e.g., under a belt or snug waist band.
470 471 472	 Subjects will be advised to closely monitor their CGM for the first 8 hours following the insertion of each SteadiSet. If CGM is uncorrectable per the hyperglycemic management guidelines, the subject will be instructed to call the study center for guidance.
473 474	 Subjects will be given guidelines with detailed procedures on what to do if prolonged elevated CGM glucose or other signs that infusion set failure might have occurred (Section 3.2).
475 476	Subjects will be instructed to contact the study site before removing an infusion set that has been worn for less than 7 full days.
477 478	 Subjects will be instructed to retain all parts of the used infusion set and label and return to the clinic.

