981	8.4.1 Clinical Events Committee	
982 983 984	Clinical Primary and Secondary Endpoint events will be adjudicated by the Clinical Events Committee (CEC). The CEC will be made up of the Medical Monitor, Lead Investigator and one independent diabetes expert.	
985 986 987 988	The CEC will adjudicate endpoint events based on review of all available information that is relevant to determining whether protocol-defined clinical endpoint events have occurred during the study as outlined in the CEC Charter. Operational details will be defined in a separate Clinical Events Committee SOP document.	
989	8.4.2 Primary Efficacy Endpoint	
990 991	Percentage of successfully-inserted SteadiSet infusion sets (i.e., not removed within 8 hours of insertion) that are not withdrawn from use prior to 7 days (168 hours) due to either (1), (2), or (3):	
992 993	 Blood Glucose value ≥250 mg/dL with ketones >1.0 mmol/L, in the absence of illness or other physiological stress. 	
994 995 996 997	2. Blood Glucose value ≥250 mg/dL for at least 60 minutes duration, 3 hours or more following a snack or meal event AND failure to respond to up to 2 adequate corrective boluses delivered by the pump with a fall of at least 50 mg/dL. In the absence of BGM testing immediately prior to or following a corrective bolus then CGM values will be used for the primary endpoint analyses.	
998	3. Investigator advises the infusion set should be replaced to assure subject's safety.	

999	8.4.3 Safety Endpoints		
1000 1001 1002	The incidence, severity, and relationship to the investigational device of all reported adverse events (serious and non-serious including DKA and severe hypoglycemia) from day of insertion through day of device removal for each wear period.		
1003		8.4.4 Key Secondary Endpoint	
1004 1005 1006 1007 1008	Proportion (%) of SteadiSet infusion sets withdrawn from use at any time following insertion prior to 7 days (168 hours) as evidenced by one or more of the following device failure modes. NOTE: infusion set removals prior to 168 hours due to miscalculation of date and/or time, along with other removals that cannot be ascribed to the investigational device performance, are excluded from this proportion calculation.		
1009 1010	1.	Infusion set failure as defined in the Primary Endpoint (including any such removals occurring during the first 8 hours following set insertion)	

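### Protocol 1.4 establishes set failure under a six-hour rule that no primary endpoint text lists; unless criterion 3 or the CEC captures such a set, the primary Kaplan-Meier analysis censors it

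*Protocol*

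**What the plan says.** **The rule.** Protocol 1.4 sets out steps for hyperglycemia with ketones at or below 1.0 mmol/L. One branch begins "If the fingerstick BG has responded to the second correction bolus with a fall of at least 50 mg/dL" and, if glucose is still 250 mg/dL or more, calls for hourly rechecks. The next step is the six-hour rule: if fingerstick glucose does not get under 250 mg/dL "within six (6) hours from initial hyperglycemic event (i.e., 9 hours after a meal event) infusion set failure is established".

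**The endpoint.** The primary endpoint is given in the Protocol Summary, Protocol 1.3.1, Protocol 8.4.2 and SAP 5.2. Each lists three removal reasons:
- criterion 1: glucose of 250 mg/dL or more with ketones above 1.0 mmol/L;
- criterion 2: sustained glucose of 250 mg/dL or more that does not fall by 50 mg/dL after up to two correction boluses;
- criterion 3: "Investigator advises the infusion set should be replaced to assure subject's safety".

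None has a six-hour clause. The Summary adds "See Section 1.4 Subject Hyperglycemia Management and Infusion Set Removal Guidelines for additional details"; the other three texts do not.

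**Censoring.** Protocol 8.6 censors early removals that do not meet the stated criteria. SAP 6.2 does the same and ties the criteria to SAP 5.2.

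**Site contact and adjudication.** When a set is deemed failed before 174 h, Protocol 1.4 requires the subject to contact the "study site to confirm set failure prior to removing the infusion set". Protocol 3.1.2 likewise has subjects told to "contact the study site before removing an infusion set that has been worn for less than 7 full days". If site personnel "are not available the subject should remove and replace the infusion set", contact and a structured interview follow afterwards. Under Protocol 8.4.1 the CEC's task is "determining whether protocol-defined clinical endpoint events have occurred during the study".

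**The concern.** A set in the six-hour branch with ketones at or below 1.0 mmol/L does not meet criterion 1. Because glucose did fall by 50 mg/dL, it does not meet criterion 2 either. One part of the protocol calls it failed, while the analysis text, read literally, censors it.

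Kaplan-Meier assumes that a censored set would have gone on to survive like the sets still in use. A set removed because the protocol declared it failed is not such a set. If these sets are meant to count, censoring them favours the device in each insulin-type test against 75%.

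The classification could also depend on circumstance. The same event might count under criterion 3 when the investigator is reached and advises replacement, and be censored when nobody is available and the subject acts alone.

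**Working it through.** **1. How narrow the gap is.** All of these must hold:
- starting fingerstick of at least 250 + 50 = 300 mg/dL, since glucose fell by at least 50 and is still 250 or more;
- ketones never above 1.0 mmol/L;
- removal after 8 h and before 168 h;
- no investigator advice to replace the set;
- no capture by the CEC.

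**2. The plan's power figure, reproduced first.** Inputs (Protocol 8.3, SAP 4): 120 subjects per insulin type, 12 wears, within-subject correlation 0.4, null 75%, true 83%, two-sided 5%.
- Design effect = 1 + 11 × 0.4 = 5.4; effective n = 1,440 / 5.4 = 266.7.
- Null SE = √(0.75 × 0.25 / 266.7) = 0.0265; alternative SE = √(0.83 × 0.17 / 266.7) = 0.0230.
- Continuity-corrected power = Φ[(0.08 − 1.96 × 0.0265 − 1/(2 × 266.7)) / 0.0230] = 87.2%.
- With 9 wears, effective n = 1,080 / 4.2 = 257.1 and power is 85.8%.

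These match the stated 87% and 86%. The power figure is not in question; the inputs are reused below.

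**3. Bias if such sets should count.** Let S be true 7-day survival counting six-hour failures as events, and g the share of all sets that fail only by that rule and are censored. The documents give no value for g; 0 to 1% is an assumption.
- All censored at the start: bias = S·g/(1 − g).
- Proportional hazards: bias = S^(1 − g/(1 − S)) − S.
- All censored just before 168 h: bias = g.

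Example, S = 0.75 and g = 1%: 0.75 × 0.01 / 0.99 = 0.76 points; 0.75^0.96 − 0.75 = 0.87 points; 1.00 point.

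| g | Sets of 1,440 | Share of failures (S = 75% / 83%) | Bias in points, S = 75% (start / PH / late) | Bias in points, S = 83% (start / PH / late) |
|---|---|---|---|---|
| 0 | 0 | 0 | 0 | 0 |
| 0.25% | 3.6 | 1.0% / 1.5% | 0.19 / 0.22 / 0.25 | 0.21 / 0.23 / 0.25 |
| 0.5% | 7.2 | 2.0% / 2.9% | 0.38 / 0.43 / 0.50 | 0.42 / 0.46 / 0.50 |
| 1% | 14.4 | 4.0% / 5.9% | 0.76 / 0.87 / 1.00 | 0.84 / 0.91 / 1.00 |

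**4. Chance of wrongly concluding above 75%, per insulin type.** By normal approximation the estimate must exceed 0.75 + 1.96 × 0.0265 = 0.802. At a true 75% under proportional hazards (start-to-late range in brackets) the chance is 2.5% at g = 0, 3.0% (2.9–3.1%) at 0.25%, 3.5% (3.4–3.7%) at 0.5% and 4.9% (4.5–5.4%) at 1%.

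**5. Simulation check.** This used Kaplan-Meier with a subject-level bootstrap. Assumptions: percentile 95% interval, beta-binomial wears with correlation 0.4, 120 subjects × 12 wears, failure times uniform after 8 h. There were two runs, of 1,500 and 1,600 replicates, with Monte Carlo SE 0.4–0.7 points. The lower limit exceeded 75% in 3.0–4.1% of replicates at g = 0, 5.1–5.6% at 0.5% and 6.9–7.6% at 1%. Mean estimates in the larger run were 0.750, 0.755 and 0.759. The percentile bootstrap starts slightly above 2.5%, and both methods show roughly a doubling at g = 1%.

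**The case against.** **Capture is likely.** Site contact is required before removal, and a site that confirms failure and has the set replaced is close to criterion 3. When staff are not reached, the later interview is recorded in the eCRF, so the CEC would have the facts. The Summary also attaches Section 1.4 to the endpoint. This stands as a reason to expect few affected sets. It does not settle their status: confirming failure is not the same as advising replacement for safety, the Summary's pointer does not list the rule, and SAP 6.2 censors by SAP 5.2 alone. The CEC Charter and SOP may resolve it, but they are not among the documents.

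**The estimand is open.** Section 1.4 is a set of guidelines and uses 174 h for site contact, not the endpoint's 168 h. It may be partly an operational rule that was never meant to define events. This stands: bias exists only relative to an estimand that counts these sets, so the claim is conditional.

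**Planned outputs would reveal the cases.** A reader might infer that nothing planned bears on the effect. The documents do not support that. SAP 6.2 tabulates the crude 7-day proportion and removal reasons by insulin type, and SAP 8 tabulates CEC determinations. Item 7 of the key secondary endpoint (SAP 5.3, analysed under SAP 6.3.1) can count device-attributable failures of insulin delivery. Together these help to bound the effect. None isolates it in the primary Kaplan-Meier estimate, because the crude proportion mixes all early removals and the key secondary endpoint adds other failure modes.

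**Conclusion.** The inconsistency is real: Protocol 1.4 establishes a failure that no primary endpoint text lists, and the censoring rules follow the lists. The consequence is conditional. If six-hour removals are meant to be failures and some escape both criterion 3 and the CEC, censoring them is informative and raises 7-day survival.

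On the assumed range of 0 to 1% of sets, the bias is 0 to about 1 point, against the 8-point distance between 75% and 83%. At 1%, the upper-side error per insulin type goes from 2.5% to about 5% by normal approximation, or from 3.0–4.1% to 6.9–7.6% in the simulation. At or below 0.5% of sets the effect is small: at most half a point of bias.

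A reader might infer that the primary result is biased upward, or by several points. At a true 75%, proportional hazards would give 1.1 to 6.8 points if 5% to 30% of failures were of this kind. The documents support neither inference: they give no frequency, capture may be complete, and the effect may be zero. Severity is minor to moderate, with medium confidence.

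**What to change.** - **Reconcile the text.** Align Protocol 1.4 with Protocol 1.3.1, 8.4.2 and 8.6 and with SAP 5.2 and 6.2. No position is taken here on which clinical rule is right.
- **Fix the classification before analysis.** State whether a removal before 168 h under the six-hour rule is an event or censored in the primary analysis. Apply the same answer whether or not site staff were reached first, and have the CEC apply it.
- **Add one prespecified sensitivity Kaplan-Meier analysis per insulin type.** Keep everything in the primary analysis: criteria 1, 2 and 3, the 8-hour successful-insertion exclusion and the same bootstrap. Change only the status of CEC-determined six-hour-rule removals: failures if the primary censors them, censored if the primary counts them. Retaining criterion 3 matters, because dropping it would change two things at once and could raise the estimate.

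**Cost.** Wording changes and one extra run per insulin type, using removal reasons and CEC determinations already planned. One of the two estimates may be slightly less favourable.
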